10.7.3.2 Hepatitis B Test

Subjects with a history of hepatitis B virus (HBV) infection should be monitored monthly with a quantitative polymerase chain reaction (PCR) test for HBV DNA. Monthly monitoring should last until 12 months after last dose of acalabrutinib. Any subject with a rising viral load (above lower limit of detection) should discontinue study drug and have antiviral therapy instituted and a consultation with a physician with expertise in managing hepatitis B. Listing of subjects with any hepatitis B test will be provided.

10.7.4 Vital Signs

Summary statistics (mean, standard deviation, median, and range) will be produced for vital signs at baseline, maximum, change from baseline to maximum, last value, and change from baseline to last value.

To be included in the table, a subject must have both a baseline value and a value for the given post-baseline time point.

10.7.5 ECOG Performance Status

Change of ECOG from baseline to the maximum score during the treatment will be provided as shift tables.

10.7.6 Electrocardiogram

ECG data is collected at screening. The investigator assessment of clinical significance categorized as normal, abnormal but not clinically significant, and abnormal clinically significant will be summarized. The number of subjects with corrected QT interval (QTc) greater than 480 msec will also be provided. A listing of subject with abnormal and clinically significant baseline ECG results or QTc> 480 msec will be produced.

11 CHANGES FROM PROTOCOL-SPECIFIED ANALYSES

There is no major change from protocol-specified analyses.

13 APPENDICES

13.1 Definitions

13.1.1 Study day

The study day will be calculated in reference to the date of first dose date. Study Day 1 is defined as the date of first dose of acalabrutinib. For assessments that occur on or after first dose date, study day is defined as (date of assessment – date of first dose + 1). For assessments that occur prior to first dose date, study day is defined as (date of assessment – date of first dose). There is no Study Day 0.

13.1.2 Simplified MIPI Score

The simplified MIPI score will be derived based on baseline values of 4 prognostic factors: age, and ECOG, LDH, white blood cell (WBC). Points will be assigned to each of these factors as presented below and the score will be derived by adding the points for all 4 factors. A score of 0-3 indicates low risk, 4-5 indicates intermediate risk, and 6-11 indicates high risk (Hoster 2008).

Points	Age (y)	ECOG	LDH ULN*	WBC, 10 ⁹ /L
0	<50	0-1	<0.67	<6.7
1	50-59	-	0.67-0.99	6.7-9.9
2	60-69	2-4	1.0-1.49	10.0-14.9
3	≥70	-	≥1.5	≥15.0

^{*}LDH relative to upper limit of normal.

13.1.3 Refractory Disease

Refractory disease is defined as a lack of at least a partial response to the last therapy before study entry (Wang 2013). Refractory disease will be assessed based on the response to the last MCL treatment regimen a subject received prior to study entry and will be categorized as Yes, No. Subject without achieving at least PR or with unknown response to the last treatment regimen prior to study entry will have a value Yes.

13.1.4 Extranodal Disease and Bone Marrow Involvement at Baseline

The extra nodal sites of lymphoma data reported on 'Disease History' CRF will be used. Subjects with any sites/extra nodal notations box checked other than 'None', 'Spleen' or 'Waldeyer's/Tonsil, Naso-oropharynx' will be considered to have extranodal disease at baseline. The detail extranodal sites will be summarized in the baseline characteristics table.

Acerta Pharma Confidential Page 22 of 28

Data reported on 'Bone Marrow Biopsy and Aspirate' CRF will be used to derive bone marrow involvement for subgroup analysis. Subjects with bone marrow biopsy and aspirate result box checked 'Not Involved' at baseline based on any method of assessment will be considered to have no bone marrow involved at baseline. Subjects with result box checked 'Involved', 'Indeterminant' or 'Other' will be considered to have bone marrow involvement as a conservative approach.

13.1.5 Gastrointestinal Disease at Baseline

Data reported on 'Disease History' CRF page will be used. Subjects with GI (gastrointestinal) box checked in the sites/extra nodal notations field will be considered to have gastrointestinal disease at baseline.

13.1.6 Tumor Bulk, Bulky Disease, and Tumor Burden at Baseline

Data reported on the CRF page lesion assessment will be used to derive these parameters.

Tumor bulk is defined as the largest diameter of a lymph node.

Tumor burden is defined as the sum of the product of diameters of all target lesions at baseline.

13.1.7 Adequate Disease Assessment

The adequate disease assessment is defined as having sufficient evidence to correctly indicate that progression has or has not occurred, as assessed by investigator. The adequate disease assessment should have response recorded other than 'Unknown/NA' in the 'Response Assessment' CRF page. Clinical assessment of PD without any objective evidence will not be considered as adequate disease assessment.

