Up to 6 measurable lymph nodes (only target lesions > 1.5 cm in the longest diameter may be assessed), clearly measurable in 2 perpendicular dimensions, will be followed as target lesions for each subject. Measurable sites of disease should be chosen such that they are representative of the subject's disease. In addition, selection of target lesions should be from as disparate regions of the body as possible when these areas are significantly involved. If additional lesions are present but are not included in the target lesion assessment, they can be added as non-target lesions followed throughout the study. The cranial-caudal measurement of the spleen and longest diameter of the liver will be assessed at screening and all subsequent response evaluations.

A central imaging vendor will be used to provide independent radiologic assessments for the purposes of confirming disease progression, while investigator assessment will be used for confirming the primary endpoint. The measurements from the central imaging vendor will not be reported back to the site.

The CT portion of a PET/CT may be submitted in lieu of a dedicated CT; however, certain radiographic requirements are needed for acceptance, as described in the Site Radiology Manual, provided separately from this protocol. Magnetic resonance imaging (MRI) may be used for subjects who are either allergic to CT contrast media or have renal insufficiency that per institutional guidelines restricts the use of CT contrast media. If MRI is used, the MRI must be obtained at baseline and at all subsequent response evaluations. If MRI is required for any other reason, this must be discussed with the study medical monitor first.

De-identified copies of all radiology results may be requested by the sponsor.

Minimal Residual Disease (MRD) Testing

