4.4 FOLLOW-UP FOR PROGRESSION AND SURVIVAL

Discontinuation Follow-up (DFU)

Subjects who discontinue for reasons other than progressive disease will be followed approximately every 24 weeks from the end of study treatment until disease progression or the start of alternative anticancer therapy, whichever occurs first, to assess survival and the use of alternative anticancer therapy. During this period, scans will be done approximately every 24 weeks.

Long Term Follow-up (LTFU)

Once subjects progress or start use of alternative anticancer therapy—for all subjects who have not withdrawn consent—they will be contacted approximately every 24 weeks by clinic visit or telephone, to assess survival and the use of alternative anticancer therapy until death or lost to follow up. At the time of the planned final analysis and additional milestone analyses, a survival sweep may be conducted. All subjects who are on study and not known to have died before the survival sweep may be contacted at that time.

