5.0 STATISTICAL METHODS OF ANALYSIS

5.1 GENERAL CONSIDERATIONS

Descriptive statistics (including means, standard deviations, and medians for continuous variables and proportions for discrete variables) will be used to summarize data as appropriate.

Response Assessment

Response assessments will be done by the investigators and independently assessed by the IRC. The IRC will conduct response evaluations in accordance with the IRC charter (provided separately from this protocol). The response and disease progression criteria are provided in [Section 4.2](#).

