5.5.3 Analysis of Efficacy Parameters

Primary Efficacy Endpoint

The primary efficacy endpoint is the ORR as assessed by investigators. The ORR is defined as the proportion of subjects achieving either a PR or CR, according to the Lugano Classification for NHL ([Cheson 2014](#)), as assessed by investigators. The corresponding 95% two-sided confidence interval will be derived.

Secondary Efficacy Endpoints

Duration of Response

The DOR is defined as the interval from the first documentation of CR or PR to the earlier of the first documentation of objective MCL disease progression or death from any cause. Kaplan-Meier methods will be used to estimate event-free curves and corresponding quantiles (including the median).

Progression-free Survival

PFS is defined as the interval from the start of acalabrutinib therapy to the earlier of the first documentation of objective MCL disease progression per investigator assessment or death from any cause. Kaplan-Meier methods will be used to estimate the event-free curves and corresponding quantiles (including the median).

Overall Survival

The duration of OS will be measured from the time of first study drug administration until the date of death. Subjects who are known to be alive as of their last known status will be censored at their last date known to be alive. Kaplan-Meier methodology will be used to estimate overall survival curves and corresponding quantiles (including the median).

IRC-assessed Endpoints per Lugano Classification

ORR, DOR, and PFS assessed by the IRC per Lugano Classification will be analyzed using the same analysis methods described for investigator-assessed endpoints. The discordant responses assessed by the investigator and IRC using Lugano Classification will be provided.

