10.6.2.1.4 IRC-assessed Endpoints per Lugano Classification

[figure not shown]
ORR, DOR, and PFS assessed by the IRC per Lugano classification are defined similarly as those assessed by the investigator.

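### IRC-assessed PFS and DOR have no IRC rule for an adequate assessment and no re-analysis for subjects whose progression only the investigator called

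*SAP*

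**What the plan says.** **Adequacy and censoring.** SAP 13.1.7 holds the only definition of what counts as adequate: "The adequate disease assessment is defined as having sufficient evidence to correctly indicate that progression has or has not occurred, as assessed by investigator". Its data source is the investigator's form: "The adequate disease assessment should have response recorded other than 'Unknown/NA' in the 'Response Assessment' CRF page". The DOR and PFS tables in SAP 13.3 and 13.4 censor at the last such assessment, except for the PFS rows censored at first dose because a baseline or post-baseline assessment is missing.

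**IRC versions.** SAP 4.2.1 lists IRC-assessed ORR, DOR and PFS as secondary endpoints. SAP 10.6.2.1.4 says only that they "are defined similarly as those assessed by the investigator". Protocol 5.5.3 adds: "ORR, DOR, and PFS assessed by the IRC per Lugano Classification will be analyzed using the same analysis methods described for investigator-assessed endpoints". Protocol 5.4 leaves the details of censoring to the SAP. A charter, which is a separate document, governs the reads: "The IRC will conduct response evaluations in accordance with the IRC charter" (Protocol 5.1).

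**Scanning after progression.** Protocol 3.8 takes subjects with confirmed progression off treatment. Protocol 4.1.20 says of the central read: "The measurements from the central imaging vendor will not be reported back to the site". Under Protocol 4.4, follow-up with scans is for subjects who stopped for reasons other than progression. "Once subjects progress or start use of alternative anticancer therapy", contact covers survival and further treatment only. The Appendix 4 schedule shows CT under discontinuation follow-up and none under long-term follow-up.

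**The concern.** Two gaps meet here.

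The first is a missing rule. If 13.1.7 is applied literally to an IRC endpoint, a subject can be censored at a visit that the investigator could judge but the IRC could not read. If it is applied in spirit, the programmer must supply the substitution.

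The second matters more. The site does not receive the central measurements, and nothing requires scans to continue until the IRC calls progression. Suppose the investigator calls progression and the IRC does not. The subject can then leave treatment and move to follow-up without scans, and the IRC analysis censors at the last adequate assessment. Kaplan-Meier assumes that censored subjects have the same future risk as those still followed. A subject just judged by the site to be progressing may well have a higher risk. If so, IRC PFS and DOR come out too long, and the plan has no analysis showing by how much.

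**Working it through.** **Plan's own figure.** The documents state no figure for bias in IRC PFS or DOR and no investigator/IRC discordance rate, so there is nothing to reproduce. What follows is an illustration under stated assumptions.

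**Inputs.**
- Scans at weeks 8, 16 and 24, then every 24 weeks (Protocol 4.1.20). A 12-week interval was also run, because SAP 3.1 gives 8 to 12 weeks.
- Median PFS of 13.9 months, with 7.4 and 16.6 as alternatives. These come from the ibrutinib phase 2 study described in Protocol 1.3.
- Minimum follow-up of about 14 months (Protocol 5.6), so the 12-month rate does not depend on accrual.
- Assumed: exponential progression times. In a share q of subjects the investigator calls progression one scan before the IRC would, scanning stops, and the IRC outcome is censored at that scan. Deaths are not modelled.

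**Formula.** Let c be the chance of IRC progression between two scans, given none before. From the second scan on, a share qc is censored at the previous scan, and the events fall from c to (1-q)c. The Kaplan-Meier factor becomes [1 - qc - (1-q)c] / (1 - qc) = (1-c) / (1-qc). The censored estimate is therefore the full-scanning estimate divided by the product of the (1-qc) terms.

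**Numbers: median 13.9 months, 24-week scans.** The last scan before 12 months is week 48 (11.04 months). S(t) = 2^(-t/13.9) gives 0.912, 0.832, 0.759 and 0.577 at weeks 8, 16, 24 and 48. So c is 0.0877 for the second and third scans and 0.2406 for the fourth.

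| q | Product of (1-qc) | 12-month IRC PFS | Shift from 57.7% |
|---|---|---|---|
| 10% | 0.9912² × 0.9759 = 0.959 | 60.1% | 2.5 points |
| 20% | 0.9825² × 0.9519 = 0.919 | 62.8% | 5.1 points |
| 30% | 0.9737² × 0.9278 = 0.880 | 65.6% | 7.9 points |

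A simulation of 100,000 subjects per setting agrees: 57.6% with full scanning, and 60.1%, 62.7% and 65.5% with the loss of scans.

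**Range over all three medians and both scan intervals (simulation).**
- 12-month rate: too high by 2.3 to 2.9 points at q = 10%, 4.6 to 6.1 at 20%, and 7.2 to 9.7 at 30%.
- Kaplan-Meier median (12-month accrual assumed): no shift at 10%; 0 to about 2.8 months at 20%; 0 to about 5.5 months, or to not reached, at 30%.
- Investigator-only progression unrelated to IRC risk (13.9-month median only): with 11% to 38% of subjects stopped this way, the 12-month rate moves by 0 to 0.1 points.

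**What the proposed sensitivity analysis would give.** In the table's setting, counting the investigator call as an event moves a share q of the week-72 progressions to week 48. With S(72 weeks) = 0.438, the 12-month rate is 0.577 - q(0.577 - 0.438), which is 56.3%, 54.9% and 53.5%. Together with the censored estimates, these bracket the full-scanning value of 57.7%.

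**The case against.** The other side has real points, and they rule out four stronger readings.

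- **That labelling endpoints are biased.** A reader might infer this because SAP 4.1 discusses labelling and the IRC together. It names ORR only. ORR is a proportion of the All-treated Population (SAP 10.6.1.2), and the censoring rules do not touch it. SAP 5 tests no formal hypotheses, so what is at stake is estimation of secondary endpoints.
- **That IRC endpoints are censored on the wrong data.** The SAP does not say so. Its wording can be read as replacing the investigator by the IRC throughout, and the charter may spell this out. The fault is an unwritten rule.
- **That the plan has no check.** SAP 10.6.3 summarises censoring reasons and reports discordant responses. SAP 13.4.2 gives a PFS analysis that counts progression and death after new therapy. Investigator PFS and DOR are reported alongside, and deaths without new therapy stay events. But none of these re-estimates IRC PFS or DOR for investigator-only progression. SAP 13.4.2 cannot recover progressions that were never scanned, and DOR has no sensitivity analysis.
- **That upward bias is certain, with the median stretched by 1/(1-d) for a discordant share d.** That shortcut gives 11% at d = 10%. It assumes a constant-hazard estimate with every discordant case an IRC event lost. Under Kaplan-Meier on the scan grid, the median does not move at 10%.

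It can also be said that scanning need not end at the first suspicion. Protocol 3.8 allows close observation, and Protocol 4.2 lets treatment continue to a confirming exam at least 2 weeks later. Both are permissive and judged at the site, so they narrow the gap without closing it. Protocol 4.1.22 keeps subjects on study procedures up to objective progression whether or not new therapy has begun, but does not say whose call counts. It also conflicts with Protocol 4.4 and Appendix 4 footnote r, which end scans at new therapy.

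**Conclusion.** The point holds as a conditional risk to two secondary endpoints, IRC PFS and IRC DOR. The documents support the route: one investigator-based definition, no central measurements returned to the site, no scans in long-term follow-up, and no analysis aimed at the resulting censoring.

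Direction and size are not known. Upward bias needs investigator-first discordance that is linked to IRC risk; where the IRC calls progression first, no event is lost. Over assumed discordance of 10% to 30%, the effect on 12-month IRC PFS runs from about 0 points (no link) to about 10 points (full link). Deaths that count as events would reduce it. DOR was not simulated separately; the same mechanism applies because its censoring rows are the same. The absence of a written IRC adequacy rule would, alone, be a matter of missing detail. What makes the point worth acting on is that a cheap analysis of data already collected would bound the effect.

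**What to change.** 1. **Add a sensitivity analysis to SAP 13.3 and 13.4.** For IRC PFS and DOR, count investigator progression as an event, at its date, when no later IRC-evaluable scan exists.
2. **Report a separate censoring reason.** In the IRC censoring summary, show investigator progression without IRC progression on its own line, so that the reader sees how many subjects are involved.
3. **Clarify SAP 13.1.7.** State that for IRC endpoints an adequate assessment is an IRC timepoint response other than not evaluable.
4. **Reconcile the protocol.** Sections 4.1.22 and 4.4 and Appendix 4 footnote r should agree on follow-up after new therapy and say whose progression call applies.

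The analysis cost is one extra Kaplan-Meier analysis per endpoint, one line in a summary table and one sentence of definition. No extra scans or reads are needed. The sensitivity analysis is conservative, since some investigator-only calls are not true IRC events, so it should be presented as a lower bound beside the main IRC estimate and not in its place.

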13.2 Imputation Rules for Partial or Missing Death Dates

If death year and month are available but day is missing:

- If mmyyyy for last contact date = mmyyyy for death date, set death date to the day after the last contact date.
- If mmyyyy for last contact date < mmyyyy for death date, set death date to the first day of the death month.
- If mmyyyy for last contact date > mmyyyy for death date, data error and do not impute.

If both month and day are missing for death date or a death date is totally missing, do not impute and censor the subject survival time.

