5.4 MISSING DATA HANDLING

General Considerations: Subjects lost to follow-up (or who dropped out) will be included in statistical analyses up to the point of their last evaluation.

Duration of Response and Progression-free Survival: Data for subjects without disease progression or death will be censored at the date of the last tumor assessment and before the initiation of alternative anticancer therapy. The censoring rules details will be provided in the Statistical Analysis Plan (SAP).

Overall Survival: Data for subjects who have not died will be censored at the date of the last date known to be alive.

Safety: Missing or partial start and end dates for AEs and concomitant medications will be imputed according to prespecified, conservative imputation rules. No other imputation of values for missing data will be performed.

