9 MISSING VALUES

9.1 Safety Data

Imputation of partial dates will be made for AE onset and stop dates, start and end dates of concomitant medication, start date of subsequent anticancer therapy, date of initial diagnosis and death date. If dates are completely missing, no imputation will be made. For any partial date with missing year, no imputation will be made.

The general rule for imputation is:

- If only day is missing, then the 15th of the month will be used.
- If only year is present, then June 30th will be used.

If such imputation date for initial diagnosis is on or after date of first dose, the date of first dose -1 will be used. If such imputed date for subsequent anticancer therapies is before the date of last dose, the date of last dose +1 will be used.

If the imputed date is for an AE start date and is in the same year and month as the first dose date but before the first dose date, then the first dose date will be used, or if the imputed AE start date is after the AE end date, then the AE end date will be used. If the imputed date is for an AE start date and is in the same year and month as but after the last dose date + 30 days, then the last dose date + 30 days will be used.

If the imputed date is for an AE end date and is after the death date, the date of death will be used, or if the imputed AE end date is before the AE start date, the AE start date will be used.

Acerta Pharma Confidential Page 11 of 28

Statistical Analysis Plan

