9.2 Efficacy Data

The method for handling missing data is described in the definition for each of the efficacy endpoints. Every effort will be made to obtain complete dates for deaths. In the event of a partial or missing death date, the algorithm in Appendix13.2 will be used.

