10.6.2.1.3 Overall Survival

The duration of OS will be measured from the time of first study drug administration until the date of death from any cause. Subjects who are known to be alive as of their last known status will be censored at their last date known to be alive. The detail censoring rules for OS are summarized Appendix 13.5.

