13.5 Censoring Rules for Overall Survival

Situation	Outcome	Date	Event Description/ Censoring Reason
Death on or before data cutoff	Event	Date of death	Death
Alive before data cutoff	Censored	Date subject last known to be alive	Alive on or before data cutoff
Death after data cutoff	Censored	Date of data cutoff	Alive on or before data cutoff
Alive on or after data cutoff	Censored	Date of data cutoff	Alive on or before data cutoff
Withdrew consent prior to data cutoff	Censored	Date of discontinuation from study participation as reported on study exit CRF	Withdrew consent
Lost to follow-up prior to data cutoff	Censored	Date subject last known to be alive	Lost to follow-up

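### SAP 13.2 censors known deaths whose date is missing, against the SAP's own OS definition and event table, which biases OS upward on average; separately, the year-only AE start rule can push on-treatment events out of the TEAE window

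*SAP*

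**What the plan says.** **Death dates.** SAP 9.2 assigns the efficacy rule: "In the event of a partial or missing death date, the algorithm in Appendix13.2 will be used". In 13.2, a death missing only its day is imputed and kept as an event. If month and day are both missing, or "a death date is totally missing, do not impute and censor the subject survival time". If the last contact falls in a later month than the recorded death, 13.2 calls it a data error and stops there, with neither a date nor an outcome.

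Elsewhere the SAP defines OS censoring differently. Section 10.6.2.1.3 reads "Subjects who are known to be alive as of their last known status will be censored at their last date known to be alive". In the 13.5 table, "Death on or before data cutoff" is an event. The protocol agrees. Section 5.4 has "Data for subjects who have not died will be censored at the date of the last date known to be alive", and 5.5.3 has "The duration of OS will be measured from the time of first study drug administration until the date of death".

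SAP 9.1, on safety data, also puts death dates under its own imputation rule. Its list of dates to be imputed includes "start date of subsequent anticancer therapy, date of initial diagnosis and death date".

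**AE start dates.** SAP 9.1 states "If only year is present, then June 30th will be used". It then moves an imputed start to first dose, or to last dose + 30 days, only when the imputed date shares the calendar year and month of that limit. A start imputed later than the AE end date is moved back to the end date. SAP 10.7.1 defines treatment-emergent as first dose to 30 days after last dose. Protocol 5.4 promises conservative imputation for AE dates.

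**The concern.** A missing date does not undo a death. Censoring assumes that the subject's later risk resembles that of subjects still under follow-up. For someone already known to be dead this is false, so the censoring is informative and lifts the Kaplan-Meier curve. OS is a secondary efficacy endpoint of a single-arm trial, so the estimate is read at face value, with no control arm to share the error.

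The rule is also incomplete. Section 13.2 gives no censoring date, and 13.5 has no row for an undated death; some of its rows censor at last known alive and others at data cutoff. With 9.1 and 13.2 both covering death dates, one death could be dated 30 June for safety and censored for OS. The OS event count could also differ from the number of deaths reported under 10.7.1.

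The AE rule errs in the same favourable direction. Whether a year-only event counts as treatment-emergent depends on where 30 June falls relative to dosing, and the errors lean towards exclusion.

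**Working it through.** **1. Provisions side by side**

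| Provision | Known death, month/day or whole date missing |
|---|---|
| SAP 13.2 | Censored, no date given |
| SAP 10.6.2.1.3 | Not in the group described for censoring (known alive) |
| SAP 13.5 | Event, if on or before cutoff |
| Protocol 5.4 | Not in the group described for censoring (not died) |

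The first three rows come from one document, so a difference in protocol version cannot explain the conflict.

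**2. Size of the OS effect.** The plan states no figure for OS or for missing dates, so there is none to reproduce. From the documents: n = 117, final analysis about 14 months after last enrolment (SAP 8), survival contact about every 24 weeks (Protocol 4.4). Assumed: exponential survival, 12-month OS of 85% or 75%, uniform 10-month entry (follow-up 14 to 24 months), last contact uniform over the 24 weeks before death, and 3%, 5% or 10% of deaths undated.

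*Expected deaths* = 117 × {1 − [exp(−14λ) − exp(−24λ)]/(10λ)}, with λ = −ln S(12)/12.
- 85%: λ = 0.01354; 117 × [1 − (0.8273 − 0.7225)/0.1354] ≈ 26, so 1 to 3 undated.
- 75%: λ = 0.02397; 117 × [1 − (0.7149 − 0.5625)/0.2397] ≈ 43, so 1 to 4 undated.

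*Hand check.* Censoring a fraction m of deaths scales the estimated hazard by about (1 − m), so S(18) becomes S(18)^(1−m).
- S(18) = 0.85^1.5 = 0.784. With m = 0.10: 0.784^0.9 = 0.803, a rise of 1.9 points.
- S(18) = 0.75^1.5 = 0.650. With m = 0.10: 0.650^0.9 = 0.678, a rise of 2.9 points.

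*Simulation* (2000 replicates, Monte Carlo SE at most 0.04). Mean change in S(18) against true dates, in points, for 3% / 5% / 10% undated:

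| Handling | 12-month OS 85% | 12-month OS 75% |
|---|---|---|
| 13.2, censored at last known alive | +0.56 / +0.93 / +1.87 | +0.80 / +1.32 / +2.75 |
| 13.2, censored at data cutoff | +0.66 / +1.08 / +2.15 | +1.05 / +1.73 / +3.56 |
| Event at proposed early date, year known | −0.02 / −0.03 / −0.04 | −0.02 / −0.03 / −0.06 |
| Event at latest possible date, year known | +0.08 / +0.16 / +0.33 | +0.15 / +0.25 / +0.52 |

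With no year known (3% and 10% undated), an event at last known alive + 1 day gives −0.03 to −0.13, or −0.05 to −0.18 if every last contact is a full 24 weeks before death. Dating the death at cutoff gives +0.34 to +1.99.

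*Other assumptions* (median OS 18, 36 or 60 months; 12-month accrual; cutoff 14 or 54 months after last enrolment; read at 12 to 36 months). Mean bias under 13.2, censoring at last contact, was +0.2 to +0.7 points with 2% undated, +0.6 to +1.7 with 5%, and +1.1 to +3.6 with 10%. It was positive in every scenario. Individual estimates fell below the true-date estimate in 0 to 6% of replicates, so the direction holds on average and not in every dataset. Events at last contact + 1 day gave −0.6 to +0.3 points.

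**3. AE start rule, checked against every calendar day (non-leap year)**
- *Start of treatment.* 30 June precedes first dose for 184 of 365 dates (1 July to 31 December). The same-month correction fires on none, because 30 June cannot precede a June first dose.
- *End of treatment.* For last doses from 1 January to 1 May (121 dates), 30 June falls after last dose + 30 days in another month and is not corrected. The correction works for 29 dates (2 to 30 May). Last doses on 2 to 31 December (30 dates) have the same gap for events in the following year.
- *Examples.* First dose 1 September 2015, event in October recorded as 2015: imputed to 30 June 2015, before treatment. Last dose 15 February 2016 (window ends 16 March), event in February recorded as 2016 with no end date: imputed to 30 June 2016, outside the window. A recorded end date of 20 February would bring it back to that day.

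**The case against.** - *13.2 is a specific exception to a general definition.* Section 10.6.2.1.3 does not say that only living subjects may be censored, and 9.2 names 13.2 as the governing algorithm. This shows which rule a programmer should follow for OS. It does not make that rule correct.
- *A wholly missing date may fall after cutoff.* This stands. The conflict is cleanest for a year-only death in a year before cutoff. If death by cutoff cannot be established, censoring at last known alive is right, and the fix keeps it.
- *The cutoff-censoring figures are a worst case.* The OS definitions point to last known alive, so those figures are the less likely reading. They remain possible because 13.2 names no date.
- *9.1 and 13.2 have separate scopes.* They are headed safety and efficacy, and reporting the incidence of deaths needs no imputed date. The overlap has little practical consequence.
- *Materiality.* The shares of undated deaths are assumptions, 9.2 commits to pursuing full death dates, and no formal hypothesis is tested (SAP 5). At 3% of 26 deaths, fewer than one subject is affected. All of this stands and limits the expected size.
- *The AE counts are calendar days, not events.* This is true. Harm also needs a year-only start in the affected year and, at the end of treatment, no end date to rescue it. Frequent early visits should make such starts few. Some such events do lie outside the window, since Protocol 6.2.1 collects SAEs before first dose and related events later. The SAP was written to Amendment 6, so the conservative standard is quoted from a later protocol version.

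**Conclusion.** The concern holds. SAP 13.2 states a rule that gives the wrong OS outcome for a subject known to have died by cutoff, and it conflicts with 10.6.2.1.3 and 13.5 of the same document. The bias is upward on average. At 18 months it is about 0.6 to 2.8 points if 3% to 10% of deaths are undated and are censored at last known alive, and up to 3.6 points if censored at cutoff, against a 95% confidence half-width of about 7.7 to 8.9 points. These sizes rest on assumed survival, follow-up, contact gaps and missing shares. With very few undated deaths the effect is small. The median is mostly not reached in the 18-month scenarios (by 24 months in about 1% of replicates at 85% and 15 to 16% at 75%), so no claim is made for it there.

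The AE gap is also real. The start-of-treatment correction can never act on a year-only date, and the end-of-treatment correction acts on few. Its frequency is unknown and probably low. The primary ORR analysis is untouched. The SAP should be corrected because the errors favour the product and are cheap to remove.

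**What to change.** **OS (SAP 13.2, 13.5, 9.1)**
1. Count a death known to have occurred by cutoff as an event even if month and day, or the whole date, are missing. Date it at the later of last known alive + 1 day and, where the year is known, the first day of that year.
2. Query deaths flagged as data errors. If unresolved, treat the month as unknown and apply rule 1.
3. If death by cutoff cannot be established, censor at last known alive, and add that row to 13.5.
4. Add a sensitivity analysis at the latest possible date: 31 December of the known year, capped at cutoff, or cutoff itself if no year is known.
5. Remove death date from the 9.1 list.

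**AE starts (SAP 9.1, year-only dates)**
1. If the year is the first-dose year and 30 June precedes first dose, use first dose, unless the AE ended before first dose or was reported as a pre-dose SAE.
2. If the year is that of last dose + 30 days and 30 June is later, use last dose + 30 days, unless other recorded information places onset later. Name the eCRF fields for both exceptions so that they can be programmed.
3. Keep the end-date clause, and leave the same-month rule for dates with a known month.

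**Cost.** SAP wording, one table row, a few lines of code and one extra OS run. OS and TEAE results may look slightly less favourable. The early death date carries a small bias of its own: 0.02 to 0.18 points downward at 18 months, and between −0.6 and +0.3 points at the other time points and assumptions tried. The latest-date analysis shows how far the result depends on that choice.
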